Appendix A Study Procedure Calendar

1.0 BACKGROUND

1A. The need for more mechanism-based therapy for atrial fibrillation: AF is the most common sustained cardiac arrhythmia affecting 2-5 million adults in the U.S. at an estimated cost of over 26 million dollars per day. With the aging of the population, the projected number of people affected with AF is estimated to be 12 million by 2050. The AF epidemic is further complicated by the lack of effective therapies. Despite recent advances in catheter-based and surgical treatments for AF, antiarrhythmic drugs (AAD) remain the mainstay of treatment for most patients with symptomatic AF. However, response in an individual patient is highly variable and carries risks of proarrhythmia and extracardiac toxicity. The poor efficacy of AAD is due to the poor understanding of the underlying pathophysiology and failure to target therapy to underlying mechanisms. The current strategy for a trial of AAD therapy focuses primarily not on efficacy, but on the side-effect profile of available membrane active drugs. There is little evidence-based data to assist the physician in selecting the most appropriate AAD for a particular patient. Over the last decade, genetic studies have provided important insights into the molecular mechanisms of AF, and our data suggest that genetic factors also contribute to variable drug actions. Given that the current success rate for AADs in AF is ~50% over a 6-12 month period, continued research aimed at refining AAD therapy such that underlying mechanisms are targeted is a major research priority in this field and our study will contribute to achieving this goal.

1B. Role of "leaky" RyR2 Ca release channels in AF pathophysiology: To better understand the molecular pathophysiology of AF, it is important to place it in the context of common arrhythmia mechanisms such as focal ectopic activity and reentry. Ectopic activity can be triggered by early afterdepolarizations (EADs), delayed afterdepolarizations (DADs), or enhanced automaticity. Rapid focal activity in the pulmonary veins (PVs) can not only initiate AF but sustain it. High frequency firing drivers or rotors or a single localized reentrant circuit can also give rise to the irregular atrial discharge that is typical for AF. Atrial fibrillatory activity may also be caused by multiple fixed and functional circuits that are time and space dependent. While the cellular mechanisms causing paroxysmal AF in humans are clearly multifactorial, experimental evidence from our group as well as others suggest that in mouse models Ca leak mediated by RyR2 Ca release channels is one important mechanism responsible for triggering of this form of the arrhythmia. Since Ca leak has been demonstrated in atrial tissue from patients with persistent and paroxysmal AF, but the causal relationship to human AF remains controversial, the overarching goal of this application is to test the hypothesis that leaky RyR2 channels confer increased susceptibility to paroxysmal AF that can be targeted therapeutically.

1C. Are "leaky" RyR2 channels a common downstream consequence of genetic AF risk variants? Recent insight into underlying AF mechanisms has been advanced by the identification of common and rare genetic variants associated with AF. Linkage analyses and candidate gene approaches have identified mutations in a variety of genes encoding cardiac ion channels, gap junction proteins, and signaling molecules. In contrast, genome-wide association studies (GWAS) have identified and validated 9 common AF susceptibility alleles, with several loci on chromosome (chr) 4q25 having the strongest association with AF (relative risk 1.39-1.72). Although the mechanism for this association remains uncertain, the locus is adjacent to the paired-like homeodomain transcription factor 2 (PITX2) gene which is critical for cardiac development, and reduced Pitx2 expression generates AF risk in mice. Given how commonly leaky RyR2 channels are found in studies of human AF, and that individuals carrying 4q25 risk alleles respond better to Class IC drugs flecainide and propafenone, both of which also inhibit RyR2 channels, this raises the hypothesis that PITX2 variants and possibly other rare AF-linked variants may initiate a cascade of cellular signaling events that ultimately leads to deranged RyR2 gating, which then contributes to AF by increasing Ca leak, generation of DADs and triggered activity. Hence, such derangement of Ca handling may constitute a common electrophysiological mechanism by which common genetic variants increase susceptibility to paroxysmal AF. To investigate this hypothesis, we will conduct a proof-of-concept clinical trial whereby the role of Ca leak for paroxysmal AF will be tested in humans by comparing AF suppression in the clinical EP laboratory. (R)- and (S)-propafenone have varying degrees of RyR2 channel inhibition and will therefore be used as tools to provide the first evaluation of whether RyR2 Ca leak contributes to AF inducibility in humans.

2.0 Rationale and Specific Aims

The overarching aim of our study is to test the hypothesis that RyR2 blockade is beneficial for preventing AF induction in humans with paroxysmal AF. We have received an NIH R01 award to evaluate the efficacy of RyR2 channel blockade to prevent inducible AF or atrial flutter (AFL) in patients undergoing an AF ablation. We will test the role of *RyR2* channel blockade by comparing drugs with variable *RyR2* action: (*R*)-propafenone, (a combined RyR2 and Na channel blocker), and (*S*)-propafenone (largely devoid of *RyR2* inhibition).

Specific Aim: To test the hypothesis that (*R*)-propafenone is superior to (*S*)-propafenone in suppressing induction of AF/AFL by a rapid atrial pacing protocol.

Rationale: Recent human studies have shown that paroxysmal forms of AF are associated with increased Ca leak from intracellular Ca stores and RyR2 dysfunction. But, it remains controversial if this abnormal Ca leakiness is mechanistically important for AF risk in humans. In mice, enhanced diastolic Ca release mediated by loss of the Ca-binding protein Casq2 can cause AF by promoting regional Ca elevations and DADs. Furthermore, inhibition of spontaneous Ca release with (*R*)-propafenone prevented AF by reducing the rate of DADs and triggered atrial activity, whereas Na channel blockers without RyR2 blocking properties (S-propafenone and lidocaine) were much less effective. These data suggest that RyR2 blocking properties are important for therapeutic efficacy against AF caused by leaky RyR2. The general approach for this study will utilize a rapid atrial pacing protocol to induce AF in subjects undergoing AF ablation. Subjects referred for AF ablation will be randomized to either (*R*)-propafenone, (*S*)-propafenone, or placebo (vehicle) in a double blind, randomized fashion. A single 10-minute infusion of intravenous (*R*)- or (*S*)-propafenone or placebo (vehicle) will be given at the start of the ablation procedure before a rapid atrial pacing protocol is performed to test inducibility of AF.

3.0 Animal Studies and Previous Human Studies

3.1: (R)-propafenone is the most potent inhibitor of spontaneous Ca release among clinically-approved AADs. We recently screened clinically available AAD for activity against spontaneous Ca release due to leaky RyR2 channels using permeabilized ventricular myocytes from Casq2-/- mice. In this assay, cell membrane permeabilization excludes any confounding drug effects on cell membrane ion channels (*i.e.*, Na channels) on Ca storage and release. We found that (*R*)-propafenone was the most potent inhibitor of spontaneous Ca waves (Fig. 1). The (*S*)-enantiomer of propafenone, which has significantly less activity against RyR2 channels, was essentially ineffective against Ca waves (Fig. 1). This is an intriguing finding, because (*R*)-propafenone inhibits the metabolism and elimination of (*S*)- propafenone, leading to much higher levels of (*S*)-propafenone compared to (*R*)-propafenone during chronic administration in patients, which may limit the efficacy of racemic propafenone currently used to treat AF patients.

3.2: (R)- and (S)-propatenone as tools to determine the role of RyR2 channel block for preventing AF induction. If leaky RyR2 channels render atria susceptible to AF induction, as suggested by mouse models with mutant RyR2 or loss of Casq2, then agents with RyR2 channel blocking properties should have superior

efficacy compared to agents that do not. Consistent with its higher potency suppressing Ca release in vitro (Fig. 1), we recently reported that (R)-propatenone exhibited superior efficacy compared to (S)propafenone lidocaine and for suppressing spontaneous Ca release, DADs and pacing-induced AF in Casq2-/- mice (Fig. 2). Furthermore, (R)propafenone was significantly more effective than Na channel blockers without RyR2 blocking properties (lidocaine, S-propafenone) in preventing CPVT in Casg2-/- mice, and in suppressing spontaneous Ca elevations and DADs in Langendorff-perfused rabbit ventricles. Unlike other experimental RyR2 blockers, (R)- and (S)-propatenone are already in clinical use as

Figure 1: Suppression of Ca wave activity by AADs.

the racemic, and therefore will be used to test our hypothesis that leaky RyR2 channels confer AF risk that can be targeted therapeutically in humans.

3.3 Increased AF risk due to chr4q25 SNPs near

PITX2. While the link between 4q25 SNPs and altered PITX2 expression in humans remains controversial, mouse models support a causal role of reduced Pitx2 expression for increased AF susceptibility. The initial report by the Martin lab attributed increased AF susceptibility in heterozygous Pitx2+/- mice to failure to suppress a left-sided pacemaker. Pitx2c, the major cardiac isoform, suppresses sinoatrial node (SAN) specific gene expression in the left atrium (LA) by binding to and repressing Shox2. Shox2 is

essential for SAN development, and Pitx2+/- mice show increased expression in the LA. This is intriguing; because in mice and humans Pitx2c is expressed after birth only in the LA and in the PVs. Together with a recent study demonstrating that Pitx2 regulates expression of ion channels (including RyR2) in the adult mouse LA, these data suggest that Pitx2 plays a role beyond regulating SAN gene expression in the adult LA. However, published studies have not investigated whether RyR2 Ca leak contributes to AF in Pitx2 mice. Furthermore, due to restricted expression of Pitx2, an effect on the RyR may be localized to LA and PV region and we therefore will determine the origin of AF in this model as shown in Fig. 3.

Chromosome 4q25 SNPs modulate differential response to AADs in patients with AF. Here, we examined whether symptomatic response to AAD is modulated by the three common AF risk loci on chr4q25 (near *PITX2*), 16q22 (in *ZFHX3*), and 1q21 (in *KCNN3*). We studied 478 (discovery cohort) and 198 (validation cohort), age and gender matched Caucasian patients with AF. Clinical variables such as age, hypertension, and lone AF failed to predict response to AADs. However, a 4q25 WT SNP was associated with successful symptom control (OR 2.97, 95% CI 1.42-6.21, P=0.003). Furthermore, individuals who carried a variant 4q25 SNP responded better to class I (flecainide or propafenone) than class III (>95% sotalol) AADs in both the discovery and validation cohorts (Table 1). These findings provide additional rationale for our study as they suggest that common AF risk variants predict differential response to AAD.

Figure 3: Posterior atrial activation mapping during AF. Right panel: Anatomical origin of focal AF in Casq2-/- (n=7)

3.3 (R)-propatenone prevents AF induction in Pitx2+/- heterozygous mice. Pitx2+/- mice were kindly provided by [name], Baylor Univ. Consistent with literature reports, AF inducibility at baseline was 67% in *Pitx2*+/- mice using atrial burst pacing (Fig. 3). Administration of (*R*)-propatenone (5 mg/kg i.p.) completely prevented AF in *Pitx2*+/- mice (Fig. 4).

3.4 The Vanderbilt AF Ablation Registry (VAFAR). To demonstrate the feasibility of performing a clinical trial in patients undergoing AF ablation, we present data from a clinical and genetic bio-repository (VAFAR) that was established by Dr. [name] (Co-investigator)

Table 1. Differential response to AADs based on 4q25 SNP genotype. ⁵²			
Discovery Co	hort		
Drug class	Wild type	Minor allele	P-
	(n=309)	carriers (n=90)	value
Class I	87 (28%)	37 (41%)	0.02
Class III	222 (72%)	53 (59%)	0.02
Validation Cohort			
Drug class	Wild type	Minor allele	Р
	(n=97)	carriers (n=46)	
Class I	37 (39%)	30 (67%)	0.01
Class III	60 (61%)	16 (34%)	0.02

in 2011. VAFAR has prospectively enrolled over 900 patients undergoing AF ablation. Uniform protocols for enrollment, blood collection, storage, DNA extraction, intra-procedural electrophysiologic data collection, and clinical follow-up are in place.

3.5 VAFAR demonstrates that 4q25 risk allele carriers have impaired response to AF ablation. In 2013, we examined atrial tachyarrhythmia recurrence (AF/AFL, or atrial tachycardia [AT]) following 378 catheter-based AF ablations in VAFAR). The final cohort consisted of 311 patients (median age 60 years [IQR 52-66]; 47% paroxysmal; 10% lone AF). The overall recurrence rate over 18-months follow-up was 53%. Using an additive genetic model, a graded gene-dose

Figure 4: R-propafenone prevents AF induction in *Pitx2*+/- mice.

response was detected based on the number of 4q25 risk alleles (P=0.037) such that heterozygous risk allele carriers suffered a 21% earlier recurrence of AT/AF (survival time ratio 0.79 [95% CI: 0.62-0.99]), and homozygous risk allele carriers a 39% earlier recurrence (survival time ratio 0.61 [0.37-1.0]). These findings suggest that common 4q25 AF risk alleles modulate response to ablation therapy in patients with predominantly paroxysmal AF.

4.0 Inclusion/Exclusion Criteria

Table 2: Eligi	bility Criteria
----------------	-----------------

Inclusion	Exclusion
atrial fibrillation	long-standing persistent AF
≥ 18 years of age	presents in AF/AFL the morning of the ablation procedure
undergoing AF ablation	 the presence of any of the following in a patient without a permanent pacemaker or ICD: a) sick sinus syndrome indicated by the inability to previously tolerate an antiarrhythmic drug due to bradycardia b) sinus bradycardia with HR <50 bpm at the time of study drug administration c) right bundle branch block, left bundle branch block, or bifascicular block d) PR > 280 ms, or history of 2nd or 3rd degree AV block
	concomitant use of CYP3A4 inhibitors and CYP2D6 inhibitors
	previous surgical or catheter ablation for AF or MAZE procedure
	amiodarone use within 3 months prior to enrollment
	AAD (other than amiodarone) within 5 half-lives prior to AF ablation
	expected life span < 1 year
	creatinine clearance <30 ml/min
	reversible cause of AF (ie. thyrotoxicosis)
	unrevascularized coronary artery disease
	Canadian Class IV angina
	left ventricular ejection fraction <40%
	New York Heart Association Class III or IV symptoms

previous heart transplantation
planned heart transplantation or ventricular assist device
cardiac/thoracic surgery \leq 6 months prior to enrollment
severe asthma or COPD
Breastfeeding

5.0 Enrollment/Randomization

Recruitment and informed consent: Eligible subjects will be identified through StarPanel. A member of the study team will request an introduction from the clinical staff, if the patient agrees. Following the introduction, the team member will approach the patient prior to AF ablation. Information describing the study, why the research is being done and what will be learned will be provided. The risks as described above will be delineated. The benefits will be described as general scientific knowledge, along with potential treatment advances. No direct immediate benefit to the subjects is anticipated. Informed consent will be documented with the subject's signature using an IRB-approved consent form for this protocol.

Randomization: This will be a double-blind, randomized study. Eligible subjects will be randomized according to a permuted block scheme with a block size of balancing interval, varying randomly according to the outcome of a computer-generated random number. This ensures that the cumulative number of assignments to each treatment (R-propafenone, S-propafenone, or placebo/vehicle) will be in balance after each block of assignments had been made. A statistician will design the randomization table and enable the randomization tool within REDCap. After a patient enrolls for the study, the study nurse will determine the treatment assignment using the randomization tool in REDCap. The day prior to the ablation procedure, the study nurse will notify IDS to prepare the study drug. The morning of the AF ablation procedure, the study nurse will pick up the study drug from the IDS.

An initial set of 6 patients received (R)- or (S)-propatenone at a rate of 1mg/kg to establish subject safety. This was open-label and not randomized. The data was reviewed with the DSMB on Dec 1, 2016. The DSMB recommended continuing the study with the 1mg/kg dose.

The study drug will be administered via a peripheral i.v. at a rate of 1mg/kg (maximum of 100mg) over 10 minutes. This will occur following induction of general anesthesia at the start of the procedure (Table 3). [name] will remain blinded to the treatment assignment as he is responsible for performing the study pacing protocol, electrogram interpretation, and interval measurement.

Table 3. Time Table for Study Protocol During AF Ablation

Time Elapsed (hrs:mins)	Standard of Care Activities	Research-only Activities
0:00→0:45	General anesthesia + TEE	
0:45→0:55	Sterile Prep and Drape	
0:55→1:00	 Operator Scrubs Official Time-out 	Study Drug Infusion Starts (0:55)
1:00→1:10	Venous Sheaths Placed	Study Drug Infusion Ends (1:05)
1:10→1:20	CS Catheter Placed	
1:20→1:25		 Blood Sample Drawn + TEE EP Study (AVNERP, AERP) Rapid Atrial Pacing Protocol 1° Endpoint Determined End of Research Protocol
1:25→end	AF ablation proceeds according to standard of care procedures	

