6.0 Study Procedures

Encounter 1: Enrollment and Informed Consent

• Performed by study nurse in VU outpatient clinic or inpatient setting

Encounter 2: Day of AF Ablation

- Ablation will be scheduled by the patient's physician according to clinical availability and is often offset by 1-60+ days from time of enrollment. The scheduling of the AF ablation procedure and post-procedure care are determined by the availability of the operator and patient according to standard of care practices.
- AF ablation will be performed according to standard of care practice by the patient's physician. Table 3 summarizes an estimated time frame for the clinical activities and simultaneous performance of the study protocol
- After the patient arrives in the operating room, they will be undergo standard of care preparation for surgery including sterile drape and administration of general anesthesia using endotracheal intubation and mechanical ventilation.
- A transesophageal echocardiogram (TEE) is performed as standard clinical practice by the cardiac anesthesiolgy attending physician immediately following intubation. This is performed to exclude the presence of a left atrial appendage thrombus and to document the presence of any pericardial fluid at baseline. The TEE is then used later in the procedure to assist in visualization of the interatrial septum for transseptal puncture. As part of the research protocol TEE pictures of the LV will be recorded to allow for offline measurement of LV contractility.
- "Time out" will be performed at the start of the case by the primary operator. Immediately following timeout, the study drug infusion will be started (1 mg/kg over 10 minutes; maximum dose 100 mg).
- 15 minutes following completion of the study drug infusion, blood will be collected from central venous sheaths that are placed at the beginning of the case. Blood will be drawn from the sheaths immediately before the AF induction protocol. This will be to enable measurement of serum propafenone levels at the time of AF induction testing. Blood will be delivered to the core laboratory for Cardiovascular Translational and Clinical Research for DNA extraction and serum/plasma storage.
- Next, repeat TEE recordings of the LV will be performed.
- The AF ablation procedure will be performed as per standard of care by the primary operator and clinical team. [name] and a study nurse will perform the study protocol.

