 - Some patients will develop AF/AFL during the standard clinical EP study. If it sustains >30 seconds it will be counted toward the primary endpoint, and the research AF induction pacing protocol will not be performed.
 - Standard-of-care monitoring following an AF ablation is inpatient 23-hour continuous cardiac telemetry observation with specialized cardiac-trained nursing care. Cardiac-trained nurse practioners remain in the hospital overnight and communicate with the electrophysiology fellow on call at night for any patient care issues. Intravenous access is maintained post-procedure during their hospitalization.

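### The trial is called double-blind, but section 5.0 has the study nurse determine the assignment and states masking only for the pacing investigator

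*Combined protocol and SAP*

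**What the plan says.** Sections 2.0 and 5.0 of the protocol describe a double-blind randomised comparison of (R)-propafenone, (S)-propafenone and a vehicle placebo. Section 5.0 sets out the handling. A statistician builds a permuted-block table with randomly varying block size in REDCap. After a patient enrols, "the study nurse will determine the treatment assignment using the randomization tool in REDCap". Then: "The day prior to the ablation procedure, the study nurse will notify IDS to prepare the study drug". The nurse collects the drug from IDS on the morning of the procedure.

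One masked role is stated. A named investigator (name removed) "will remain blinded to the treatment assignment as he is responsible for performing the study pacing protocol", and also reads the electrograms and measures the intervals.

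Section 6.0 gives enrolment and consent to the study nurse and says that the ablation date "is often offset by 1-60+ days from time of enrollment". In the procedure room, a named investigator "and a study nurse will perform the study protocol".

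Two exclusions in Table 2 (section 4.0) can be settled only on the day: a patient who "presents in AF/AFL the morning of the ablation procedure", and, in patients without a pacemaker or ICD, "sinus bradycardia with HR <50 bpm at the time of study drug administration".

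Section 9.0 lets the PI withdraw a patient for four reasons. Reason (iii) rests on the primary operator's judgement. Reason (iv) is spontaneous AF, atrial tachycardia or flutter before the study protocol is complete. Section 6.0 says of AF/AFL arising during the clinical EP study: "If it sustains >30 seconds it will be counted toward the primary endpoint".

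**The concern.** Section 5.0 does not say whether REDCap shows the nurse an arm or a code, or whether the dispensed infusions look alike and carry neutral labels. The ordinary meaning of determining the assignment is that the nurse learns it. That would matter in two places.

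- **Enrolment.** A nurse who knows the earlier arms and also consents later patients can partly predict the next assignment under permuted blocks. This weakens allocation concealment.
- **After assignment.** If the arm is known for days or weeks before ablation, and in the procedure room, it could influence who stays in the trial or how adverse events are judged. A blinded electrogram reader protects the reading of the endpoint. That reader cannot correct a difference between arms in who reaches the endpoint.

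**Working it through.** The plan gives no figure on this point to reproduce. The check sets the text side by side and adds two illustrations of scale.

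**1. Roles and stated masking**

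- Pacing investigator: stated to be blinded (5.0).
- Study nurse: consents patients (6.0), determines the assignment, notifies IDS and collects the drug (5.0), and helps perform the study protocol (6.0). No masking stated.
- Primary operator: can prompt withdrawal under 9.0 (iii). No masking stated.
- Investigator judging adverse-event causality (8.0): no separate masking statement.
- Product: vehicle placebo (2.0) and preparation by IDS (5.0). These are implicit masking features. Matched appearance, coded labels, REDCap access limits and a code-break route are not described.
- Serum propafenone: sampled just before induction (6.0). Results would separate placebo from active drug. Who may see them, and when, is not stated.

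**2. Timing**

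Assignment happens at an unstated time after enrolment, so it can precede ablation by the whole 1-60+ day interval. Moving it to the day before shortens that window. It still comes before both day-of exclusions.

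**3. Predictability at enrolment (illustration)**

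Assumptions: the nurse knows all earlier arms; the block size is fixed and known; the ratio is 4:4:1, taken from the section 10.0 totals (108 + 108 + 27 = 243; 108/27 = 4). With a, b and c assignments left in the block and n = a + b + c, the expected number of correct guesses is

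E(a,b,c) = max(a,b,c)/n + (a/n)E(a−1,b,c) + (b/n)E(a,b−1,c) + (c/n)E(a,b,c−1), with E(0,0,0) = 0.

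Dividing by the block size gives the share guessed correctly:

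- Block of 9: 60.4% correct, 16.0% known with certainty.
- Block of 18: 56.5% and 8.7%.
- Block of 27: 54.6% and 6.0%.
- No knowledge, always naming one active arm: 4/9 = 44.4%.

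Block sizes are not given, and the randomly varying size in section 5.0 would lower the first three lines.

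**4. Selective loss after assignment (illustration)**

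Assumptions: yes/no endpoint, 108 per active arm, 50% truly inducible in both (54 patients), and k inducible patients lost from one arm only. The rate in that arm becomes (54 − k)/(108 − k). The standard error of the difference is √(2 × 0.25/108) = 6.80 points.

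- k = 1: 53/107 = 49.5%, shift 0.47 points, 0.07 SE.
- k = 3: 51/105 = 48.6%, shift 1.43 points, 0.21 SE.
- k = 5: 49/103 = 47.6%, shift 2.43 points, 0.36 SE.
- k = 10: 44/98 = 44.9%, shift 5.10 points, 0.75 SE.

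For k = 5 the shift is 3.40 points (0.54 SE) at 30% inducibility and 1.46 points (0.23 SE) at 70%. The smallest k that takes a pooled two-proportion z from no effect to 1.96 is 16, 24 or 35 at 30%, 50% or 70%. The planned primary analysis is ordinal, covariate-adjusted and omits AFL-only patients (10.0), so these SE multiples do not carry over to it.

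**5. Section 9.0 (iv) against section 6.0**

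Table 3 places the EP study among the research activities, before the end of the research protocol. AF lasting more than 30 seconds during the EP study is an endpoint event under section 6.0. If it is judged spontaneous, it also meets reason (iv). The text gives no rule for telling the two apart.

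**The case against.** The strongest reply is that this argues from silence. The trial is declared double-blind, the comparator is a vehicle placebo, IDS prepares the drug, and REDCap may return only a code. No text gives the nurse an exclusion or withdrawal decision. Section 9.0 gives that to the PI, who may be the blinded investigator; names are removed, so this cannot be checked. The nurse who obtains the assignment need not be the nurse in the room. In Table 3, only 30 minutes pass from the start of infusion (0:55) to the end of the research protocol (1:25). Before pacing nobody knows who is inducible, so operator judgement under (iii) cannot readily pick out inducible patients.

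Most of this stands, and it limits the size of the point. It does not remove it: the procedure as written puts the assignment in the hands of a role that also enrols and assists, and nothing described keeps the arm from that role.

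Three stronger readings are tempting.

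- A reader might infer that the nurse is in fact unblinded. The documents do not say what REDCap displays.
- A reader might infer that the interim P-value of 0.075 in section 10.0 makes a few selective losses decisive. That analysis used the ordinal endpoint; its sample size, comparison and sidedness are not given, and no withdrawal counts are reported.
- A reader might infer that releasing the arm only to IDS closes the gap. It does not if the product itself reveals the arm or if drug levels circulate, and it cannot help patients already randomised.

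**Conclusion.** The point holds as a gap between the double-blind label and the stated procedure. The natural reading leaves a nurse role able to know the arm while enrolling later patients and assisting in the procedure room. Masking of the primary operator and the adverse-event assessor is not shown either.

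The actual bias cannot be sized, because no withdrawal counts are given. For the blinded-read primary endpoint it is probably small: a handful of one-sided losses moves the simplified comparison by a fraction of a standard error. That rests on the assumed yes/no endpoint, inducibility of 30% to 70%, and losses confined to inducible patients in one arm. The enrolment figures rest on a fixed, known block and so overstate predictability under varying blocks.

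The conflict between section 9.0 (iv) and section 6.0 is separate. If the drug affects spontaneous AF, withdrawing those patients can distort the comparison even under perfect masking.

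**What to change.** For patients not yet randomised:

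- Set REDCap permissions so that only IDS sees the arm; the nurse enters the subject ID.
- Have IDS dispense coded, indistinguishable infusions, with a code-break route through IDS.
- Make the assignment at the existing day-before IDS notification, not at enrolment. The two day-of exclusions will still follow it.
- Restrict access to serum propafenone results until the endpoint data are final.
- List every masked role in section 5.0.

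For all randomised patients, state what the nurse saw, and tabulate post-assignment exclusions and withdrawals by arm and reason.

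Separately, reconcile section 9.0 reason (iv) with the section 6.0 endpoint rule, so that each AF/AFL episode before the end of the protocol has one stated classification.

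The cost is a REDCap permission change and a small coding step at IDS, which already prepares the drug and is already notified the day before. The documents give no cost figures, so calling this inexpensive is a judgement. The main limit is timing: an interim analysis had been reviewed by March 2019, the number still to be randomised is not stated, and for earlier patients only reporting is possible. If REDCap already returns a code and the infusions are already masked, a few sentences in section 5.0 settle the REDCap and infusion items.
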